5.7.2 Enzalutamide Dose Modification or Delay

If a patient experiences a Grade 3 or greater toxicity or an intolerable side effect, withhold enzalutamide and CORT125281 dosing for 1 week or until symptoms improve to Grade 1 or

less, or to the patient's baseline, then resume at the same or a reduced dose, if warranted. If a dose reduction of enzalutamide is required, the dose will be decreased by 40 mg for each reduction. A maximum of 2 dose level reductions of enzalutamide will be allowed. The maximum time a patient's study treatment may be held due to toxicity is 28 days; after which the patient must be discontinued from study participation. If enzalutamide is discontinued, CORT125281 will be discontinued.

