3.3.3 Study Duration

Patients will receive CORT125281 in combination with enzalutamide until reaching a protocol-defined event of disease progression, experiencing unmanageable toxicity, or until other treatment discontinuation criteria are met (Section 4.4.1). As per PCWG3, patients with an isolated PSA rise after an initial decline who show evidence of benefit should continue treatment until radiographic or clinical progression.

All patients will be followed for progression, information on subsequent anticancer therapies (start and end date and response) and survival.

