4.4.1 Patient Discontinuation of Study Treatment

Study treatment will be discontinued in any of the following occurrences:

- Progressive disease. If the patient is experiencing overall clinical benefit, the patient may be allowed to remain on the study. Both the Medical Monitor and the Investigator must agree that this is appropriate for the patient.
- Unmanageable toxicity.
- Request for early discontinuation or withdrawal of consent by the patient.
- The Investigator decides it is in the patient's best interest to discontinue treatment and/or participation in the study. Reasons may include the following:
 - The patient requires prohibited medications or initiates treatment with another drug for treating prostate cancer
 - The patient is not adherent to the protocol

If a patient discontinues CORT125281, enzalutamide will be continued per the guidelines provided in Section 5.7.1.1. If a patient discontinues enzalutamide, CORT125281 will also be discontinued.

Patients who discontinue study treatment for reasons other than withdrawal of consent (eg, AE, Investigator decision) will undergo a Post-Treatment/ EOT Visit and EOT +30 Days Visit, and will be followed for progression and survival.

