4.4.2 Patient Withdrawal from Study/Study Completion

Withdrawal from the study (including all follow-up assessments) will occur under the following circumstances:

- Withdrawal of consent for follow-up observation by the patient
- Patient is lost to follow-up
- Study termination by Sponsor
- Death

If a patient withdraws from the study, the Investigator should complete and report the observations as thoroughly as possible up to the date of withdrawal and the primary reason for withdrawal. For patients who withdraw consent to participate in the study, every effort should be made to determine whether the withdrawal of consent was related to an AE or a specific aspect of the study.

The Investigator will ask all withdrawn patients to consent to a follow-up examination, to check that they have come to no harm as a result of taking part in the study. Provided that patients agree, they will undergo the standard medical examination and laboratory tests that they would have undergone had they completed it.

If a patient withdraws from the study without meeting study endpoints, the Investigator will immediately (within 48 hours after discontinuation) notify the Sponsor.

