5.7.1.1 Continuation of Enzalutamide After CORT125281 Interruption/Discontinuation

The following guidelines apply for enzalutamide continuation in patients who discontinue CORT125281 or have a CORT125281 dosing interruption:

1. Patients may resume enzalutamide prior to resuming CORT125281 after the Investigator discusses with the Medical Monitor. The intent is for patients to maintain the dose intensity of enzalutamide per standard practice whenever possible.
2. For patients who have not progressed on enzalutamide or second-generation anti-androgen, if CORT125281 is discontinued, enzalutamide will be continued. Following the visit of the subsequent cycle (after discontinuing CORT125281), if all toxicities attributed to CORT125281 have resolved, study visits will occur at least every third cycle until discontinuation of enzalutamide (Section 7.3.1). Upon discontinuation of enzalutamide, the patient will return for the EOT and EOT +30 Days Visits.
3. Patients previously progressing on enzalutamide or second-generation anti-androgen will discontinue enzalutamide, if CORT125281 is discontinued.

Radiographic tumor assessments (CT/MRI, bone scan) should be continued until disease progression per the SoA (Table 16).

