7.5 Post-Treatment Follow-Up Period

If the patient discontinued CORT125281 and enzalutamide for reasons other than disease progression, tumor assessments will be collected and documented until disease progression.

All patients will continue to be followed until the study endpoints are met (radiographic disease progression, SSE, and overall survival). Phone follow-up for overall survival (ie, the date and cause of death, and post-treatment information) will continue every 4 months until 2 years from the date that the last patient enrolls in the study or until all patients have completed follow-up for radiographic disease progression (whichever is later).

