7.5.2 Every 4 Months After the End-of-Treatment +30 Days Visit (\pm 10 Days)

- Record post-treatment anticancer therapies, dates of initiation, end dates, and response
- Record survival information (ie, date and cause of death), unless the patient requests to be withdrawn specifically from the study survival follow-up. This request must be documented in the patient's medical record and signed by the Investigator. The study staff may use public information source (such as county records) to obtain information about survival status only per local regulations, as appropriate.
- For patients who discontinued the CORT125281 + enzalutamide due to reasons other than disease progression, continue tumor assessments and PRO and QoL questionnaires per the schedule of procedures until disease progression

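### Protocol 5.7.2 removes a patient held 28 days for toxicity from study participation, where the rest of the protocol stops treatment and keeps him in follow-up; study treatment was probably meant

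*Protocol*

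**What the plan says.** Protocol 5.7.2 tells sites to withhold both drugs for a Grade 3 or greater toxicity or an intolerable side effect. It sets 28 days as the longest hold for toxicity, "after which the patient must be discontinued from study participation". The next sentence says that CORT125281 stops if enzalutamide stops.

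Other sections treat stopping drug and leaving the study as two separate events:

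- **Protocol 3.3.3:** "All patients will be followed for progression, information on subsequent anticancer therapies (start and end date and response) and survival".
- **Protocol 4.4.1:** unmanageable toxicity is a reason to stop study treatment. "Patients who discontinue study treatment for reasons other than withdrawal of consent (eg, AE, Investigator decision) will undergo a Post-Treatment/ EOT Visit", then the 30-day visit, then follow-up for progression and survival.
- **Protocol 4.4.2:** "Withdrawal from the study (including all follow-up assessments) will occur under the following circumstances". Four are listed: withdrawn consent for follow-up, loss to follow-up, termination by the sponsor, and death.
- **Protocol 7.5:** when both drugs stop for a reason other than progression, scans continue until progression. "All patients will continue to be followed until the study endpoints are met".

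**The concern.** Section 5.7.2 is an operative instruction with a mandatory verb, and it names a different outcome from the one that 4.4.1 and 7.5 give for the same event. A hold normally ends when toxicity improves to Grade 1 or to baseline, so a patient who reaches day 28 has ordinarily not recovered. A site that took the sentence at its word would end scans and the four-monthly survival contacts for that patient. Follow-up time would then be cut short for a reason tied to how he tolerated the treatment, which is the setting in which censoring may be informative.

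**Working it through.** No design figure is involved and there is no number in the plan to reproduce. The check sets the texts side by side and then traces what a literal reading would do to each analysis.

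**1. The texts compared**

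| Source | After a stop for toxicity |
|---|---|
| Protocol 5.7.2 | Ends study participation, mandatory |
| Protocol 4.4.1 | Ends treatment; end-of-treatment and 30-day visits, then progression and survival follow-up |
| Protocol 4.4.2 | Toxicity is 0 of the 4 listed reasons for leaving the study |
| Protocol 3.3.3 and 7.5 | All patients followed; scans to progression |
| SAP 8.1, treatment | Adverse events are 1 of 9 reasons for stopping treatment |
| SAP 8.1, study | Adverse events are 0 of the 4 named reasons for stopping the study; a fifth category is *Other* |

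**2. Are participation and treatment the same thing here?** Not safely. The investigator-decision item in 4.4.1 names treatment and participation as separate things that may be ended together or singly. Yet 4.4.1 also says of a patient who progresses with clinical benefit that "the patient may be allowed to remain on the study", where continued treatment appears to be meant. The vocabulary is loose, so the literal reading of 5.7.2 cannot be excluded.

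**3. Which was intended?** The sentence in 5.7.2 is about holding study treatment, and the next is about stopping drug. The Appendix E note on retitling 4.4.2 describes a design in which patients who stop treatment remain for long-term follow-up; I use it for intent only. Study treatment is the natural reading, but this is an inference.

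**4. What a literal reading would do**

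- **Overall survival (SAP 9.1):** censored at last contact, so earlier than planned. Protocol 7.5.2 offers a partial backstop: "The study staff may use public information source (such as county records) to obtain information about survival status", subject to local rules.
- **Radiographic PFS and duration of response (SAP 9.1, Table 3):** censored at the last adequate scan. Table 3 already censors at the last scan before new anticancer therapy, so the loss falls on patients who have not started one. For them, a death more than 119 days after the last scan would also drop out as an event.
- **Symptomatic skeletal events:** event-free patients are already censored at the end-of-study or treatment-plus-30-days visit, so little changes.
- **Clinical progression:** the event is itself treatment discontinuation for progression, so little changes.
- **DLTs:** Protocol 5.5 already counts a dose delay over 2 weeks for a related adverse event within the evaluation period. A 28-day hold exceeds that (28 > 14 days). SAP 8.8 also keeps patients who stop for toxicity in the DLT-evaluable set. The primary endpoint is little affected.
- **Disposition (SAP 8.1):** the patient would appear under adverse events for treatment, but only under *Other* for study discontinuation.

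**5. Size.** The documents give no rate of 28-day holds and no basis for signing a bias. No estimate is made.

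**The case against.** The strongest reply is that this is loose drafting across both documents, not one stray sentence against a consistent set. Protocol 8.1.2 foresees a patient withdrawn from the study because of an adverse event, Protocol 9.5.6 lists such events, and SAP 4.2.1 makes study withdrawal due to adverse events a safety endpoint. That stands. A reader might infer from SAP 8.1 that the SAP cleanly excludes toxicity as a reason for leaving the study; SAP 4.2.1 does not support that. But none of these texts makes withdrawal mandatory for toxicity or adds it to the list in 4.4.2.

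A reader might also infer that a site cannot comply with all the sections at once. That goes too far. Section 4.4.2 has its own explicit phrase for full exit, 5.7.2 uses a different and undefined one, and a site that reads it as stopping drug breaches nothing. The conflict exists on the literal reading only.

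Third, a reader might infer that the unresolved toxicity would go unwatched. Protocol 8.1.2 requires related adverse events and all serious ones to be followed until resolved or stable. Section 8.1.2.1 and Table 12 carry adverse event follow-up beyond the 30-day visit. Section 4.4.2 has the investigator ask withdrawn patients to consent to a follow-up examination. These largely answer the safety worry, though they do not replace scheduled scans or survival contacts.

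**Conclusion.** The wording mismatch is certain: the sentence is current text, and read literally it contradicts 3.3.3, 4.4.1, 4.4.2 and 7.5. That study treatment was meant is probable. Any harm is conditional on a site applying 5.7.2 literally, and none is demonstrated. If it happened, the exposure is early and possibly informative censoring of overall survival and, before new therapy, of radiographic PFS and duration of response. All three are descriptive secondary endpoints. The number of patients and the direction of any bias are unknown. This is a minor correction worth making because it is easy. It is not evidence that any planned result is biased, and it does not question the length of the 28-day limit.

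**What to change.** Reword the end of the sentence in Protocol 5.7.2 so that the patient *must be discontinued from study treatment and followed per Sections 4.4.1 and 7.5*.

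The visits, scans and survival contacts are already in the schedule of assessments, so no procedure is added and no design figure moves. A protocol amendment needs ethics re-approval (Protocol 10.1), so a clarification letter now, or inclusion in the next planned amendment, is proportionate. Whether a hold of CORT125281 alone counts towards the limit is a separate question. Section 5.7.1.1 partly answers it with its own guidance for "patients who discontinue CORT125281 or have a CORT125281 dosing interruption", and this correction does not depend on it.

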5.8 Intra-Patient Dose Escalation

5.8.1 Intra-Patient Dose Escalation of CORT125281

5.8.1.1 Dose-Determination Phase Segment 1

Patients in this part of the study who have not experienced Grade 2 or greater toxicity attributed to CORT125281 may, upon discussion with the Medical Monitor, increase CORT125281 to a dose level that has been shown to be safe and well tolerated after studying data from later cohorts. PK will be collected per [Table 20](#) to determine the impact of dose escalation on enzalutamide and CORT125281 exposures.

[figure not shown]
5.8.1.2 Dose-Determination Phase Segment 2

Patients in this part of the study will receive CORT125281 at a starting dose of 240 mg QD, with dose titration in 40-mg increments to a max dose of 320 mg QD (Arm A) or without an increase of the active dose (240 mg QD; Arm B). Patients in Arm B will receive placebo capsules, such that the patient, Investigators, and study team are blinded to the actual dose the patient is receiving.

All patients will start treatment with CORT125281 240 mg QD on Cycle 1 Day 1. Beginning on Cycle 1 Day 16, the dose will be escalated every 2 weeks, as tolerated, as shown in [Figure 3](#). If any planned dose escalation is postponed due to a transient intolerable Grade 2 toxicity, the dose may be escalated within 14 days of the planned escalation.

After the DRC has determined the RD in Dose-Determination Phase Segment 2 (Section [5.4.2](#)), patients assigned to Arm B who have not experienced dose reductions due to toxicity will then have their dose escalated in an open-label fashion per the RD regimen.

Figure 3 CORT125281 Intra-Patient Dose Escalation in Segment 2

^a. Once the dose has been modified for toxicity, re-escalation is not allowed.

5.9 Prior and Concomitant Medications

The use of any prohibited, prior, or concomitant treatments will be recorded in the eCRF along with their daily dosage, duration, and reason for administration.

5.9.1 Permitted Concomitant Therapy Requiring Caution

The following medications are permitted but must be used with caution from 1 week before the first dose of study treatment (CORT125281 or on-study enzalutamide, whichever is earlier) through the final treatment with enzalutamide:

- Moderate substrates of CYP2C9

This study allows for patients who discontinue CORT125281 to continue on enzalutamide alone (Section 5.7.1.1). The following restrictions only apply to patients on CORT125281 (ie, these medications will not be restricted in patients who are on enzalutamide alone).

Permitted medications to be used with caution from 1 week before Baseline through the final dose of CORT125281 are as follows:

- Moderate substrates of CYP2C8
- Warfarin: If co-administration of the study regimen with warfarin cannot be avoided, conduct additional INR monitoring.

- Sulfonylureas: For patients receiving sulfonylureas, conduct close glucose monitoring to assess for diabetic control.
- Corticosteroids:
 - Systemic corticosteroids. Short courses of prednisone for non–cancer-related reasons are permitted if clinically required. CORT125281 treatment should be withheld during corticosteroid administration, and the Medical Monitor should be notified.
 - Potent (Group III) topical corticosteroids should be used with caution due to the potential for systemic absorption, and the Medical Monitor should be contacted to discuss the treatment approach.

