CYP2C8 plays an important role in the elimination of enzalutamide and in the formation of its active metabolite. It is recommended to avoid strong CYP2C8 inhibitors, as they can increase the exposure to enzalutamide. CYP3A4 plays a minor role in the metabolism of enzalutamide. In vivo studies have shown that enzalutamide is a strong inducer of CYP3A4 and a moderate inducer of CYP2C9 and CYP2C19. CYP3A4, CYP2C9, and CYP2C19 substrates with a narrow therapeutic index should be avoided in patients receiving enzalutamide, as enzalutamide may decrease the plasma exposures of these drugs.

Gemfibrozil (600 mg BID) increased the area under the curve from 0 to infinity ($AUC_{0-\infty}$) of enzalutamide and N-desmethyl enzalutamide (M2, the active metabolite of enzalutamide) by 2.2-fold with minimal effect on C_{max} ([Xtandi USPI 2019](#)). Gemfibrozil is converted by metabolism to gemfibrozil glucuronide, a strong, metabolism-dependent, inhibitor of CYP2C8 with a metabolism shifted IC_{50} of 1.8 μM for inhibition of CYP2C8. Gemfibrozil glucuronide is present in plasma at high levels, the total C_{max} and unbound C_{max} for gemfibrozil glucuronide are 20 μM and 2.3 μM , respectively ([Ogilvie et al. 2006](#)).

CORT125281 is a direct inhibitor of CYP2C8 (IC_{50} of 0.59 μM). In contrast to gemfibrozil glucuronide, CORT125281 is highly bound to human plasma proteins (>99.9%). Therefore, the available free fraction of gemfibrozil glucuronide (11.5%) is approximately 115-fold greater than the free fraction (<0.1%) of CORT125281. Therefore, at initial clinical doses of CORT125281 the free drug concentrations are not expected to cause a meaningful increase in exposure to enzalutamide and metabolites.

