is required prior to initiating the first day of CORT125281. For patients currently receiving strong CYP3A4 or CYP2C8 inhibitors, a minimum wash-out period of 14 days is required prior to initiating the first dose of CORT125281. Prohibited medications are not permitted during the enzalutamide Lead-In Period during Dose-Determination Phase Segment 1, as per protocol Section 5.9.2.

- Co-administration of enzalutamide with warfarin will not be exclusionary. If co-administration of warfarin cannot be avoided, conduct additional INR monitoring
- Refer to [Appendix C](#) for examples of prohibited concomitant medications and foods

12. Toxicities of prior therapies (except alopecia) that have not resolved to NCI-CTCAE of Grade 1 or less.
13. Any other concurrent cancer or a history of another invasive malignancy within the last 3 years that has a likelihood of recurrence of >30% within the next 5 years. Adequately treated non-melanoma skin cancers or non-muscle invasive urothelial cancer or other tumors curatively treated with no evidence of disease are permissible.
14. Concurrent treatment on other Phase 1, 2, or 3 investigational treatment studies for the treatment of prostate cancer.

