5 STUDY TREATMENTS AND MANAGEMENT

Study drug is defined as CORT125281. The co-administered drug is defined as enzalutamide.

Study treatment is defined as CORT125281 and/or enzalutamide, administered according to the protocol.

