5.9.2 Prohibited Medications/Treatments/Foods

Anticancer agents including cytotoxic chemotherapy, hormonal therapy (other than LHRH analogues), immunotherapy, biologic therapy, therapeutic radiotherapy, or investigational agents are not permitted during the treatment portion of the study.

The following medications are prohibited from 1 week before the first dose of study treatment (CORT125281 or on-study enzalutamide, whichever is earlier) through the last treatment with enzalutamide (for applicable wash-out periods, refer to Section 4.2):

- Strong inducers of CYP3A4
- Strong inhibitors or inducers of CYP2C8
- Sensitive substrates of CYP3A4
- Sensitive substrates of CYP2C9
- Sensitive substrates of CYP2C19

The following are prohibited from 1 week before Baseline through the final dose of CORT125281:

- Strong inhibitors of CYP3A4
- Treatment with systemic GCs or requirement for chronic or frequently used systemic GCs for medical conditions

Anticancer Chinese medicines or herbal remedies are not allowed. Herbal products or alternative therapies that may decrease PSA levels or that may have hormonal anti-prostate cancer activity (eg, saw palmetto, PC-SPES, PC-HOPE, St. John's wort, selenium supplements, grape seed extract) are not allowed. Other herbal products or vitamin supplements are not allowed for 14 days before the first dose of study treatment and until the last PK sample collection. Vitamins/supplements (such as potassium supplements for hypokalemia) will be allowed, if clinically indicated. These should be discussed with the Medical Monitor if their use is indicated during the PK-evaluation period.

Consumption of foods and beverages containing the following substances will be prohibited as indicated:

- Grapefruit and/or Seville orange, including marmalade and juices made from these fruits from 14 days prior to the first dose of CORT125281 and/or enzalutamide and until the last treatment cycle is completed.

- Alcohol: Alcohol is known to induce CYP3A4 and may lead to reduced plasma exposure of enzalutamide. Alcohol use should be avoided from 48 hours before the first dose of study treatment and until the completion of intensive PK (Cycle 2 Day 1). Alcohol intake within the past 48 hours will be documented during study visits that include PK assessment.

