APPENDIX C: EXAMPLES OF MEDICATIONS AND FOODS THAT ARE PROHIBITED OR TO BE USED WITH CAUTION

The following medications and foods are examples of prohibited medications/foods or medications/foods to be used with caution during the study:

	Prohibited	Use with Caution
CYP3A4 Inducers	St. John's wort Carbamazepine, phenytoin, rifampin	Bosentan, efavirenz, etravirine, modafinil, nafcillin
CYP3A4 Inhibitors	Grapefruit and Seville oranges (including marmalade and juices made from these fruits) Boceprevir, clarithromycin, conivaptan, indinavir, itraconazole, ketoconazole, lopinavir/ritonavir, mibefradil, nefazodone, nelfinavir, posaconazole, ritonavir, saquinavir, telaprevir, telithromycin, voriconazole	Amprenavir, aprepitant, atazanavir, ciprofloxacin, darunavir/ritonavir, diltiazem, erythromycin, fluconazole, fosamprenavir, verapamil
CYP3A4 Substrates	Alfentanil, aprepitant, astemizole, budesonide, buspirone, cisapride, conivaptan, cyclosporin, darifenacin, darunavir, dasatinib, dihydroergotamine, dronedarone, eletriptan, eplerenone, ergotamine, everolimus, felodipine, fentanyl, indinavir, fluticasone, lopinavir, lovastatin, lurasidone, maraviroc, midazolam, nisoldipine, pimozide, quetiapine, quinidine, saquinavir, sildenafil, simvastatin, sirolimus, tacrolimus, terfenadine, tolcapant, tipranavir, triazolam, ticagrelor, vardenafil	
CYP2C8 Inducers	Rifampin	
CYP2C8 Inhibitors	Gemfibrozil	Glimepiride, tolbutamide ^a
CYP2C9 Substrates	Celecoxib, phenytoin	Warfarin ^b
CYP2C19 Substrates	S-mephenytoin, omeprazole, lansoprazole, esomeprazole ^c , clobazam	
Corticosteroids or GR modulators	Mifepristone or other GR antagonists	Topical or oral corticosteroids
QT-prolonging medications		Substitute or eliminate QT-prolonging medications, when possible (https://www.crediblemeds.org/)

BID, twice daily; CYP, cytochrome P450; GR, glucocorticoid receptor.

^a. For patients receiving sulfonylureas, conduct close glucose monitoring to assess for diabetic control.

^b. If co-administration of the study regimen with warfarin cannot be avoided, conduct additional international normalized ratio monitoring.

^c. Ranitidine 75 mg BID may be used as an alternative to a proton pump inhibitor, with the dose of ranitidine taken 1 hour after CORT125281 administration.

The above is not an exhaustive list. For a more comprehensive list or to review specific medications, see the following links:

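### Section 5.9.1 ends the warfarin/INR caution at the last CORT125281 dose, although the protocol ties that caution to enzalutamide, which some patients continue alone

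*Protocol*

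**What the plan says.** Protocol Section 5.9.1 contains two lists of medications permitted with caution.

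- The first list holds moderate CYP2C9 substrates and runs "through the final treatment with enzalutamide".
- The second list holds moderate CYP2C8 substrates, warfarin, sulfonylureas and corticosteroids, and ends at the final CORT125281 dose. Its preamble refers to patients who stop CORT125281 but continue enzalutamide, and states: "The following restrictions only apply to patients on CORT125281 (ie, these medications will not be restricted in patients who are on enzalutamide alone". The warfarin entry reads: "Warfarin: If co-administration of the study regimen with warfarin cannot be avoided, conduct additional INR monitoring".

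Other parts of the protocol bear on the same instruction.

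- Section 4.2, criterion 11: "Co-administration of enzalutamide with warfarin will not be exclusionary. If co-administration of warfarin cannot be avoided, conduct additional INR monitoring".
- Section 1.4: "enzalutamide is a strong inducer of CYP3A4 and a moderate inducer of CYP2C9 and CYP2C19". It adds that CYP2C9 substrates with a narrow therapeutic index should be avoided in patients taking enzalutamide, because their exposure may fall.
- Section 5.9.2: "Sensitive substrates of CYP2C9" are prohibited until the last enzalutamide treatment.
- Appendix C: warfarin appears under use with caution in the CYP2C9-substrate row. Its footnote repeats the INR instruction and gives no time window.
- Section 5.7.1.1, item 2: patients who have not progressed on enzalutamide or a second-generation anti-androgen continue enzalutamide when CORT125281 stops.

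**The concern.** Enzalutamide alone is a planned state in this study, and the sentence in 5.9.1 is the only concomitant-medication text written for patients in it. Read literally, it lifts the warfarin caution while the drug that the protocol names as a CYP2C9 inducer is still being taken. A site could then stop the additional INR checks, and the expected direction of the interaction, on the protocol's own account, is lower exposure to the substrate.

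Scheduled tests would not make up for this. The Section 7.3.1 assessment list for enzalutamide alone has no INR. Table 16 sends these visits to its column for Cycle 4 and beyond, where the coagulation row is blank. Visits may be as far apart as every 3 cycles. Section 7.3 schedules on-treatment INR only on Day 1 of Cycles 1 to 3, and Table 16 next marks it at end of treatment.

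What is at stake is the consistency of a safety instruction. No estimate, test or decision rule depends on it.

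**Working it through.** The plan gives no figure on this point, so the check is a comparison of texts followed by a rough count of who could be affected.

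**Does the warfarin/INR instruction apply on enzalutamide alone?**

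| Protocol text | Drug it is tied to | End of the instruction | On enzalutamide alone |
|---|---|---|---|
| 5.9.1, second list | *study regimen* (undefined) | final CORT125281 dose | lifted |
| 4.2, criterion 11 | enzalutamide | none given | applies on its wording |
| 5.9.1, first list (moderate CYP2C9 substrates) | enzalutamide, by its end date | final enzalutamide treatment | applies, if warfarin belongs here |
| Appendix C, warfarin footnote | *study regimen* (undefined) | none given | not settled |

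**Which side fits the protocol's own sorting?** Restrictions that reflect enzalutamide's CYP2C9 induction run to the last enzalutamide dose: sensitive substrates in 5.9.2 and moderate substrates in 5.9.1. Appendix C classes warfarin as a CYP2C9 substrate. Warfarin is therefore the exception, and no reason is given for it. Section 1.3.1.3.3 reports partial in vitro CYP2C9 inhibition by CORT125281 (IC50 0.8 µM). That explains a caution during CORT125281 treatment, but it is no reason to drop the caution once enzalutamide is the only drug left.

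**Who could be on enzalutamide alone?**

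- ARant-Resistant Cohort, about 20: excluded, because 5.7.1.1 item 3 stops both drugs after prior progression on enzalutamide or a second-generation anti-androgen.
- Abi-Resistant Cohort: about 20.
- Segment 1 patients treated by 18 February 2020 (Section 1.3.2.1): 2 + 3 + 7 = 12 in Cohorts 1, 2 and 3.
- Segment 2: about 20. They enter with rising PSA on enzalutamide, and 5.7.1.1 does not say whether that counts as having progressed.

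The 7 patients in Cohort 3 had no lead-in, and exclusion criterion 3 bars prior progression on enzalutamide only for patients who receive the lead-in. All 7 could therefore fall under item 3.

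- Without Cohort 3 and Segment 2: 20 + (12 − 7) = 25.
- With Cohort 3, without Segment 2: 20 + 12 = 32.
- With both: 20 + 12 + 20 = 52.

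The figure of 25 is not a strict floor. Criterion 3 bars prior second-generation anti-androgen use in Segment 1 only when urgent disease control is needed, so some Cohort 1 or 2 patients could also have progressed on such a drug.

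**How many warfarin users?** The documents give no rate. At an assumed 2% to 10%:

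- Pool 25: 25 × 0.02 = 0.5 to 25 × 0.10 = 2.5.
- Pool 52: 52 × 0.02 = 1.04 to 52 × 0.10 = 5.2.

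These are counts before multiplying by the unknown fraction who stop CORT125281 and stay on enzalutamide.

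**The case against.** The strongest reply is that the texts differ in scope and do not contradict each other. Criterion 11 is an eligibility note saying that warfarin does not exclude a patient, whereas the treatment-period windows are set in Section 5.9. This has some force. But the second half of that note is an instruction on conduct, and it names enzalutamide.

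A second reply is that caution survives elsewhere. Warfarin can be read into the first 5.9.1 list through its row in Appendix C, Section 5.9.4 points to the enzalutamide label for concomitant therapy, and Section 5.9.2 points to product labels in case of doubt. This stands as partial mitigation. A general pointer does not cancel a specific sentence addressed to exactly these patients.

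Three stronger readings are tempting, and the documents support none of them.

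- *The protocol removes INR monitoring for these patients.* It does not. Saying that a drug is not restricted is no order to stop monitoring, and the mitigating texts remain in force.
- *The Appendix C footnote is a second, independent contradiction.* Appendix C lists examples without time windows. It shows strong CYP3A4 inhibitors as prohibited with no end date, although 5.9.2 ends that ban at the final CORT125281 dose. The footnote also uses the same undefined term as 5.9.1. Section 5 says "Study treatment is defined as CORT125281 and/or enzalutamide, administered according to the protocol", but that defines *study treatment*. Where *study regimen* is used for DLT evaluability in Section 5.4, the context is the combination. Only warfarin's place in the CYP2C9 row counts, as supporting evidence.
- *Section 1.4 directly tells sites to avoid warfarin.* It does not name warfarin, and the protocol permits it with monitoring.

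**Conclusion.** The inconsistency is real and minor. Section 5.9.1 lifts the warfarin/INR caution on enzalutamide alone, whereas Section 4.2 criterion 11, the CYP2C9 statements in Section 1.4 and the end dates used for other CYP2C9 substrates all point to keeping it until enzalutamide stops. The conclusion rests on the wording of those sections and on Appendix C's classification of warfarin.

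The size is small. About 25 to 52 patients, possibly fewer, could continue enzalutamide alone, depending on how Cohort 3 and Segment 2 are classed. Under the assumed 2% to 10% warfarin use, that pool holds between about 0.5 and 5 users before any transition to enzalutamide alone is counted. The number actually affected may be zero. A reader might infer some consequence for the safety analysis or the dose decision; nothing in the protocol or SAP makes an endpoint, DLT rule or analysis depend on this instruction.

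**What to change.** At the next amendment, move the warfarin bullet in Section 5.9.1 from the second list to the first, so that it runs until the final treatment with enzalutamide. Reword it along these lines: *If co-administration of warfarin with CORT125281 and/or enzalutamide cannot be avoided, conduct additional INR monitoring.* Moving the bullet unchanged would not be enough, because *study regimen* can be read as the combination only.

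With the bullet moved, the sentence on enzalutamide alone no longer covers warfarin, and 5.9.1 agrees with criterion 11. Section 7.3.1 and the Schedule of Assessments need no change, and no scheduled test is added. The cost is an occasional extra INR check in warfarin users who stay on enzalutamide, with no effect on sample size, endpoints or analysis.
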